The cumulative incidence of clinical outcomes (stroke/ systemic embolism and major bleeding) will be calculated throughout the study period, from which the incidence or survival curves will be derived using the Kaplan Meier method. Incidence of events will be explored in clinically relevant subgroups based on sample size.

A similar analysis will be performed for the group of patients who have not presented stroke/ systemic embolism or major bleeding events to estimate the time for discontinuation events and change of treatment.

In the independent variables, the significance will be analyzed, as a level of statistical significance $p < 0.05$.

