7. RESEARCH METHODS

7.1. Study Design

Observational, descriptive study of a retrospective cohort of adult patients diagnosed with NVAF in selected Health Maintenance Organization (HMO) of Colombia. These patients will be identified from the drug claim database, whose index date of the study will be the first prescription with any of the oral anticoagulants, that is, they are patients with NVAF for the first time starting a therapy with any of the NOACs between January 1, 2013 and June 30, 2018 and follow up period will be among January 2013 to July 2019, to ensure that the last patients can provide follow-up for one year. Patients will be required to have an NVAF diagnosis before or on the index date and health plan for 6 months pre-index date (baseline period).

Following, it will be verified that the patients meet the inclusion and exclusion criteria of the study. Once patients are selected and with the index date of each patient, they will be followed-up until discontinuation, switch of treatment, death or first event of stroke/ systemic embolism, major bleeding event, death or end of follow-up. Patients who are lost to follow-up, change of HMO and do not have access to the medical record will be considered as missing (Figure 1).

Figure 1. Study Design

[figure not shown]
The information will be analyzed in two moments: (i) the period of the index date, where the baseline information of patients will be collected; (ii) and the follow-up period, during this period the clinical results will be evaluated as well as the continuation of the treatment in the study population and for specific subpopulations.

Those patients who initiated treatment with any oral anticoagulant between January 2013 and June 30, 2018 will be included. This means that patients who start warfarin and NOACs would

be included within this period. Patients who initiate NOACs within the established period and who have been exposed to warfarin before 2013 will also be included.

Only the exposure period will be considered with the initial treatment, even in those patients who were on warfarin treatment before 2013, in the latter, the follow-up will be the treatment initiation with a NOAC in case of change after 2013. Follow-up will be carried out until the patient has a switch of treatment, discontinuation, death, first stroke/ systemic embolism, or major bleeding, or until end of follow-up, June 30, 2019 (Figure 2).

Figure 2. Inclusion of Patients

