7.3.1. Definition of outcome variables

- **OAC escalation:** The dose escalation of the OAC dose will be considered as a dose frequency according to the index dose, as well as the follow-up doses. The proportion of patients experiencing "dose increase", "dose decrease" or "no change" during follow-up with respect to the index dose will be measured, and the time to dose increase or decrease will be calculated.

C
C
I

C
C
I

- **Switch of treatment:** A switch among anticoagulants will be defined as a prescription filled for non-index anticoagulants within +/- 30 days after the date of discontinuation.
- **Persistence:** Persistence will be defined as the time under OAC therapy, calculated as the time in days from the index date to the date of discontinuation or change to treatment. As previously stated, discontinuation will be defined as a change of treatment, that is, to another OAC, or when there is no evidence of a prescription for 60 days from the last supply delivered, whichever comes first.

Therefore, if a patient does not receive his next prescription for the OAC therapy within 60 days after the end of the previous prescription, it will be considered that he discontinued therapy, and the date of the last prescription will be considered as the final date of persistence.

Persistence with OAC therapy will be considered during the period of individual patient follow-up. Patients will be censored at the end of their follow-up period.

- **Major bleeding:** Patients presenting any of the following diagnoses during the follow-up period:

ICD-10	Description
I60	Subarachnoid haemorrhage
I61	Intracerebral haemorrhage
I62	Other nontraumatic intracranial haemorrhage
I690	Sequelae of subarachnoid haemorrhage
I691	Sequelae of intracerebral haemorrhage
I692	Sequelae of other nontraumatic intracranial haemorrhage
S064	Epidural haemorrhage
S065	Traumatic subdural haemorrhage
S066	Traumatic subarachnoid haemorrhage
I850	Oesophageal varices with bleeding
K250	Acute with haemorrhage

Apixaban

B0661148- NON-INTERVENTIONAL STUDY PROTOCOL

Final, 10 October 2019

ICD-10	Description
K252	Acute with both haemorrhage and perforation
K254	Chronic or unspecified with haemorrhage
K256	Chronic or unspecified with both haemorrhage and perforation
K260	Acute with haemorrhage
K262	Acute with both haemorrhage and perforation
K264	Chronic or unspecified with haemorrhage
K266	Chronic or unspecified with both haemorrhage and perforation
K270	Acute with haemorrhage

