7.7 Data Analysis

This type of analysis is descriptive and explanatory, as it depends largely on the sample size. Continuous variables will be presented as means, standard deviation or other measures of central tendency or position, while categorical variables will be presented as frequencies and percentages.

Regarding bivariate analyses of continuous variables with normal behavior, the Student's t test will be performed. In case of presenting non-normal behavior, the Mann-Withney test will be used. For variables that are continuous with several categories, analysis of variance (ANOVA) will be assessed. In the event of presenting a non-normal behavior, the multivariate analysis of

variance (MANOVA) test will be carried out. For categorical variables, the X² test will be used.

Exploratory analyses based on sample size:

The cumulative incidence of clinical outcomes (Stroke/ systemic embolism and major bleeding) will be calculated throughout the study period, from which the incidence or survival curves will be derived using the Kaplan Meier method. Incidence of events will be explored in clinically relevant subgroups based on sample size.

For the execution of the analysis, CCI and change of treatment, and missing treatments are considered as censures. Treatment comparison will be not conducted.

A similar analysis will be performed for the group of patients who have not presented stroke/ systemic embolism or major bleeding events to estimate the time for CCI change of treatment.

In the independent variables, the significance will be analyzed, as a level of statistical significance p < 0.05.

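### Kaplan-Meier for time to switch overstates the proportion who switch if switchers are kept in the cohort and stops without a switch are censored

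*Combined protocol and SAP*

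**What the plan says.** The statistical part of the abstract says that, for stroke/systemic embolism and major bleeding, "incidence or survival curves will be derived using the Kaplan Meier method". It then plans a similar analysis "for the group of patients who have not presented stroke/ systemic embolism or major bleeding events", in order "to estimate the time for discontinuation events and change of treatment". Section 7.7 repeats both steps, with the first of the two treatment events redacted. Table 1 lists switch (yes/no) and time to switch as variables separate from persistence.

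Section 7.1 fixes the end of observation: "Follow-up will be carried out until the patient has a switch of treatment, discontinuation, death, first stroke/ systemic embolism, or major bleeding", or the end of the study period. Section 7.3.1 gives the definition used for persistence: "discontinuation will be defined as a change of treatment, that is, to another OAC, or when there is no evidence of a prescription". The gap that counts is 60 days, and the earlier of the two sets the date. The same section defines a switch as a fill of a non-index anticoagulant within a 30-day window around the discontinuation date.

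Neither the abstract nor 7.7 names a competing-risk estimator.

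**The concern.** Once a patient has stopped the index drug without a switch, follow-up is over and a switch can no longer be observed within it. In the analysis of time to switch, such a stop is a competing event. Kaplan-Meier has only two ways to leave the risk set, event or censoring, so a patient who leaves at a stop is censored. The method then assumes that this patient would have gone on to switch at the same rate as those still on treatment. One minus Kaplan-Meier becomes the probability of switching in a population where nobody stops, which is not the proportion of this cohort that switches.

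The study is descriptive, so the percentage is itself the result. Treatment patterns are a primary objective, and 7.4.1 counts changes of treatment among them. The bias grows with time, and follow-up can run from January 2013 to mid-2019, about 6.5 years. A larger cohort does not reduce it.

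**Working it through.** **Inputs.** The method, the end-of-follow-up rule and the definitions come from the abstract and sections 7.1, 7.3.1 and 7.7. The documents state no switch or stopping rate, so there is no figure of the plan's to reproduce. All rates below are assumptions: constant hazards *s* for switch and *d* for discontinuation without switch, no deaths, and switchers retained.

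**Formulas at time *t*.**
- Kaplan-Meier with stops censored: 1 − exp(−*st*).
- Actual proportion switched (cumulative incidence): [*s*/(*s*+*d*)] × [1 − exp(−(*s*+*d*)*t*)].

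**Worked case, *s* = 0.10, *d* = 0.30.**
- 1 year: 1 − exp(−0.10) = 9.5%; 0.25 × [1 − exp(−0.40)] = 0.25 × 0.330 = 8.2%.
- 3 years: 1 − exp(−0.30) = 25.9%; 0.25 × [1 − exp(−1.20)] = 0.25 × 0.699 = 17.5%.

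**Range** (differences taken before rounding):

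| *s*, *d* per year | Year | 1 − KM | Cumulative incidence | Excess, points |
|---|---|---|---|---|
| 0.05, 0.15 | 1 | 4.9% | 4.5% | 0.3 |
| 0.05, 0.15 | 3 | 13.9% | 11.3% | 2.6 |
| 0.10, 0.30 | 1 | 9.5% | 8.2% | 1.3 |
| 0.10, 0.30 | 2 | 18.1% | 13.8% | 4.4 |
| 0.10, 0.30 | 3 | 25.9% | 17.5% | 8.4 |
| 0.10, 0.50 | 1 | 9.5% | 7.5% | 2.0 |
| 0.10, 0.50 | 3 | 25.9% | 13.9% | 12.0 |

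**Second grid.** This one is set by assumed true 1-year incidences: switch 2% to 20%, stopping without switch 20% to 50%. The excess at 1 year runs from 0.2 to 9.1 points. For 5% and 30%, the total hazard is −ln(0.65) = 0.431 and the switch hazard is 0.431 × 5/35 = 0.0615. Kaplan-Meier then gives 1 − exp(−0.0615) = 6.0% at 1 year against the true 5%. At 3 years it gives 16.9% against (5/35) × (1 − 0.65³) = 10.4%. One simulated cohort of 7,500 with these rates and follow-up spread over 1 to 6.5 years gave 6.2% against an Aalen-Johansen 5.2% at 1 year, and 17.3% against 10.7% at 3 years.

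**Discontinuation as defined in 7.3.1.** Either a switch or a 60-day gap is an event. In the worked case at 3 years, any discontinuation is 1 − exp(−1.20) = 69.9% and still on the index drug is 30.1%, together 100%. Switching does not bias this curve. The switch error reappears only by subtraction: 69.9% − 25.9% = 44.0% would be read as stopped without switching, when the true figure is 0.75 × 0.699 = 52.4%.

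**Exclusion as written.** Section 7.2.2 removes patients exposed to more than one OAC during follow-up. Applied literally, no switcher remains and the switch curve stays at 0%.

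**The case against.** Several points on the other side are sound.

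- A reader might infer that switch and discontinuation each distort the other's curve, and that the reported percentages would add to more than 100%. The documents do not support this. Under 7.3.1 a switch is part of discontinuation, so the discontinuation curve is valid and the two figures are nested, not additive. A total above 100% arises only if discontinuation is taken to mean stopping without a switch, which the plan does not define as an endpoint.
- A reader might also infer that the reported switch figure is bound to be too high. As written, the exclusion of patients with more than one OAC pushes it to zero. In addition, a non-index fill shortly after the discontinuation date counts as a switch under 7.3.1, yet it falls after follow-up has ended under 7.1, so true switches could be lost.
- The statement in 7.7 that a redacted item "and change of treatment, and missing treatments are considered as censures" stands with the clinical-outcome analysis, and change of treatment cannot be censored in its own analysis. That stops are censored in the switch curve is therefore an inference from 7.1 and from how Kaplan-Meier works, not an explicit rule.
- Section 7.7 places these curves among the exploratory analyses. The primary objective's examples name persistence but not switch. Yes/no variables are to be reported as plain percentages, so no text says that the switch percentage will be read from the curve.

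These points limit the scope but do not remove the issue. Time to change of treatment is planned as a Kaplan-Meier-type analysis, and its curve is naturally read as the proportion switched. Crude percentages do not replace it, because follow-up is unequal.

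**Conclusion.** The concern holds for the switch curve only, and on two conditions: switchers are retained, and patients who stop without switching are censored when their follow-up ends. One minus Kaplan-Meier then overstates the proportion who switch. Under the assumed hazards in the first table the excess is 0.3 to 2.0 points at 1 year and 2.6 to 12.0 points at 3 years. The direction follows from the method; the size depends on rates that the documents do not give. The persistence analysis under 7.3.1 is not affected by switching. The change is worth making because it is cheap and gives a percentage that means what readers will take it to mean.

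**What to change.** In the abstract and in 7.7:

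1. Keep Kaplan-Meier for any discontinuation as defined in 7.3.1 (persistence).
2. Report Aalen-Johansen cumulative incidence for switch and for discontinuation without switch, with death as a competing state. Give the estimates at fixed times from one model, so that switched, stopped without switch, died and still on the index drug add to 100%. If the persistence curve censors deaths, add a note that it will not match the sum of the two incidences exactly.
3. Add stroke/systemic embolism or major bleeding as a competing state only if the analysis is not restricted to patients without these events. Under the present restriction that state would be empty.
4. State for each analysis which exits are events, competing events or censoring.
5. Reconcile the exclusion of patients exposed to more than one OAC (7.2.2) with switch as an outcome and as an end of follow-up. Reconcile the 30-day switch window (7.3.1) with follow-up ending at discontinuation (7.1).

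The cost is revised wording and a little extra programming, possibly an R extension to SPSS. The switch figure will be lower than a Kaplan-Meier reading. Step 2 needs no new data.

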3. AMENDMENTS AND UPDATES

None

PFIZER CONFIDENTIAL

4. MILESTONES

Milestone	Planned Data
Start of data collection	November 15, 2019
End of data collection	March 31 , 2020
Data analysis	CCI [REDACTED]
Preliminary report	CCI [REDACTED]
Final study report	CCI [REDACTED]

PFIZER CONFIDENTIAL

[REDACTED]

5. RATIONALE AND BACKGROUND

Non-valvular atrial fibrillation (NVAF) is an acute or chronic heart disorder that is associated with an increase in the mortality rate, strokes and other thromboembolic events (1). This is further increased by individual conditions of patients, such as hypertension, abnormal renal or hepatic function, stroke, history of or predisposition to bleeding, people over 65, among others. (2)

One of the standard treatments for management of these patients is usually vitamin K antagonists (VKA, for example, warfarin); in the analysis of net clinical benefits of this therapy it is suggested that the effect of VKA is even more positive in patients with a high score on the HAS-BLED (hypertension, abnormal renal/liver function, stroke, bleeding history or predisposition, labile International Normalized Ratio, elderly, drugs/alcohol concomitantly) scale. (3) Another therapeutic alternative is the new oral anticoagulants (NOAC) — dabigatran, rivaroxaban and apixaban —, which according to evidence have advantages in efficacy and safety compared to warfarin (4) and even when the risk of bleeding and stroke are high, the net clinical benefit appears to be greater when compared to warfarin. (5) Likewise, there is a lower prevalence of intracranial hemorrhage and its different subtypes of patients being treated with new oral anticoagulants when compared to warfarin. (6)

While it is true there are several studies that seek to understand the characteristics of patients who were diagnosed with NVAF under different treatment options, and even subpopulation analyses, the evidence at the national level is limited, both in demographic and clinical characteristics and in treatment patterns of this population. In a retrospective descriptive study of an emergency department in a third level care center in the city of Bogota, it was observed that the main comorbidities of patients with atrial fibrillation (AF) were arterial hypertension and heart failure where most patients do not receive anticoagulation. (7) In turn, for the overall population it is estimated that the prevalence of AF in Colombia (4.8%) seems to be higher than that reported in developed countries (0.03% to 1.25%) (8), according to a study conducted in a university hospital in the country (9).

Taking into account the limited knowledge on the use of oral anticoagulants in patients diagnosed with NVAF in the country and, even more in the differences in the response to these therapies in different patient subpopulations. The purpose of this study is to assess the demographic and clinical characteristics, treatment patterns and incidence of events (discontinuation, persistence, key primary clinical outcomes) in NVAF patients that initiated OACs in study period.

6. RESEARCH QUESTION AND OBJECTIVES

Primary Objectives

- To assess demographic and clinical characteristics of NVAF patients treated with oral anticoagulants (OACs) in Colombia.
- To describe treatment patterns (eg. OAC usage, dose, concomitant medications, persistence)

Exploratory Objectives

- To descriptively assess the time to clinical events (Effectiveness and Safety Outcomes) among patients persistent on OAC therapy.

Effectiveness outcomes: First Stroke/ Systemic Embolism; CCI

Safety outcomes: Major bleeding, CCI

[figure not shown]
7. RESEARCH METHODS

7.1. Study Design

Observational, descriptive study of a retrospective cohort of adult patients diagnosed with NVAF in selected Health Maintenance Organization (HMO) of Colombia. These patients will be identified from the drug claim database, whose index date of the study will be the first prescription with any of the oral anticoagulants, that is, they are patients with NVAF for the first time starting a therapy with any of the NOACs between January 1, 2013 and June 30, 2018 and follow up period will be among January 2013 to July 2019, to ensure that the last patients can provide follow-up for one year. Patients will be required to have an NVAF diagnosis before or on the index date and health plan for 6 months pre-index date (baseline period).

Following, it will be verified that the patients meet the inclusion and exclusion criteria of the study. Once patients are selected and with the index date of each patient, they will be followed-up until discontinuation, switch of treatment, death or first event of stroke/ systemic embolism, major bleeding event, death or end of follow-up. Patients who are lost to follow-up, change of HMO and do not have access to the medical record will be considered as missing (Figure 1).

Figure 1. Study Design

[figure not shown]
The information will be analyzed in two moments: (i) the period of the index date, where the baseline information of patients will be collected; (ii) and the follow-up period, during this period the clinical results will be evaluated as well as the continuation of the treatment in the study population and for specific subpopulations.

Those patients who initiated treatment with any oral anticoagulant between January 2013 and June 30, 2018 will be included. This means that patients who start warfarin and NOACs would

be included within this period. Patients who initiate NOACs within the established period and who have been exposed to warfarin before 2013 will also be included.

Only the exposure period will be considered with the initial treatment, even in those patients who were on warfarin treatment before 2013, in the latter, the follow-up will be the treatment initiation with a NOAC in case of change after 2013. Follow-up will be carried out until the patient has a switch of treatment, discontinuation, death, first stroke/ systemic embolism, or major bleeding, or until end of follow-up, June 30, 2019 (Figure 2).

Figure 2. Inclusion of Patients

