2. ABSTRACT

Study title: Patient characteristics, treatment patterns and incidence of events (discontinuation, persistence, key primary clinical outcomes) in NVAF patients initiating OAC therapy in Colombia				
Protocol number	B0661148	Phase	4	Type
Condition/Disease	Non-valvular atrial fibrillation (NVAF)			
Number of patients	The total population of patients treated with OAC between January 1, 2013 and June 30, 2018 was analyzed in the claim dabtabase. For the purpose of the study, it contains the information of 7,500 patients, once they were verified that they met the inclusion criteria of the study.	Duration of the patients in the study	Follow-up will be performed until the patient presents a switch, discontinuation, death, event of stroke / systemic embolism or major bleeding, or until June 30, 2019.	
Country participants	Colombia	Duration of the study	8 months	
Rational and background: Non-valvular atrial fibrillation (NVAF) is an acute or chronic heart disorder that is associated with an increase in the mortality rate, strokes and other thromboembolic events (1). This is further increased by individual conditions of patients, such as hypertension, abnormal renal or hepatic function, stroke, history of or predisposition to bleeding, people over 65, among others. (2)				
One of the standard treatments for management of these patients is usually vitamin K antagonists (VKA, for example, warfarin); in the analysis of net clinical benefits of this therapy it is suggested that the effect of VKA is even more positive in patients with a high score on the HAS-BLED (hypertension, abnormal renal/liver function, stroke, bleeding history or predisposition, labile International Normalized Ratio, elderly, drugs/alcohol concomitantly) scale. (3) Another therapeutic alternative is the new oral anticoagulants (NOACs) — dabigatran, rivaroxaban and apixaban —, which according to evidence have advantages in efficacy and safety compared to warfarin (4) and even when the risk of bleeding and stroke are high, the net clinical benefit appears to be greater when compared to warfarin. (5) Likewise, there is a lower prevalence of intracranial hemorrhage and its different subtypes of patients being treated with new oral anticoagulants when compared to warfarin. (6)				

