7.2. Setting

The study will be conducted with the Audifarma patient cohort that meets the inclusion and exclusion criteria between the periods from January 2013 to June 30, 2018. The follow up period will be among January 2013 to July 2019, to ensure that the last patients can provide follow-up for one year.

This study will include the entire population in which medical records can be accessed. This will depend on the authorization of the HMOs for review of medical records. Participating patients will be followed-up until the patient has a stroke/systemic embolism, major bleeding, discontinuation, change of treatment or until the data collection period is completed.

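### Persistence has no run-out period: unless claims after the end of follow-up are read, refill-gap stops in the last 60 days or more go unrecorded and persistence is biased slightly upward

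*Combined protocol and SAP*

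**What the plan says.** **Entry and end of follow-up.** Patients enter "between January 1, 2013 and June 30, 2018" (7.1). The end of follow-up is worded in three ways:

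- "until end of follow-up, June 30, 2019" in 7.1, and "or until June 30, 2019" in the Abstract;
- "follow up period will be among January 2013 to July 2019" in 7.1, repeated in the Abstract and 7.2, with no day given;
- "change of treatment or until the data collection period is completed" in 7.2. Section 4 plans the end of data collection for March 31, 2020.

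Sections 7.1 and 7.2 give the purpose of the window as "to ensure that the last patients can provide follow-up for one year".

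**Stop rule.** Section 7.3.1 counts a change to another anticoagulant as a discontinuation. It states the 60-day gap in two ways. One counts from the last supply delivered. The other applies "if a patient does not receive his next prescription for the OAC therapy within 60 days after the end of the previous prescription". The stop is then dated to the last prescription. Patients without a recorded stop are censored at the end of their follow-up.

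**Not stated.** The visible text gives no days' supply per fill, no claims cut-off later than the end of follow-up, and no earlier censoring date for persistence. Parts of 7.3.1 and 7.7 are blacked out, so this concerns only the text that can be read.

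**The concern.** A stop is recognised only after the gap has run its course, but is dated to the start of that gap. If the data end at the cut-off, patients who stop shortly before it are treated in opposite ways. Take the 60-day count from the last delivery and a cut-off of June 30, 2019:

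- Last fill April 28, 2019: the gap completes on June 27, and the patient is a stop on April 28.
- Last fill May 5, 2019: the gap would complete on July 4, and the patient is censored as persistent on June 30, with 56 unverified days at risk.

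Time in this final window counts in the Kaplan-Meier denominator although no refill-gap event can occur in it, so the curve is pushed up. Persistence is named in a primary objective (section 6). The same stop date ends treatment time for the exploratory outcomes, so missed stops also add off-treatment days there.

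**Working it through.** **1. The plan's own figure.** June 30, 2018 to June 30, 2019 is 365 days. The stated year reproduces as calendar time.

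**2. Blind window W.** Counting from the last supply delivered: W = 60 days. Counting from the end of the previous prescription: W = 60 + days' supply. The supply is not in the documents, so 30, 60 and 90 days are assumptions.

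- Last datable stop = June 30, 2019 − W.
- Observable days for the last entrant = 365 − W.
- Share of patients without a full observable year = W / 2,007. January 1, 2013 to June 30, 2018 is 2,007 days, and uniform entry is assumed. The study size of 7,500 is from 7.5.

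| Rule | W | Last datable stop | Observable days | Share | Of 7,500 |
|---|---|---|---|---|---|
| From last supply delivered | 60 | May 1, 2019 | 305 | 3.0% | 224 |
| After a 30-day supply ends | 90 | April 1, 2019 | 275 | 4.5% | 336 |
| After a 60-day supply ends | 120 | March 2, 2019 | 245 | 6.0% | 448 |
| After a 90-day supply ends | 150 | January 31, 2019 | 215 | 7.5% | 561 |

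With an end date of July 31, 2019 the last entrant has 396 calendar days, hence 336 (W = 60), 306 (W = 90) or 246 (W = 150) observable days, all under 365. If follow-up ran to March 31, 2020, 275 days after June 30, 2019, the last entrant would have 365 + 275 − 150 = 490 observable days even with 90-day fills.

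**3. Size of the bias, pooled cohort.** Simulated Kaplan-Meier: 7,500 patients, 20 runs, uniform entry, constant stopping, end June 30, 2019, gap counted from the end of the previous prescription. The plan's rule is compared with a rule that reads later claims. Figures are percent persistent.

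| Assumed 1-year persistence | Fill | 12 months: plan − look-ahead | 3 years: plan − look-ahead |
|---|---|---|---|
| 40% | 30 d | 37.86 − 37.60 = 0.26 | 6.92 − 6.15 = 0.77 |
| 60% | 30 d | 58.17 − 57.97 = 0.20 | 22.60 − 21.20 = 1.40 |
| 80% | 30 d | 78.94 − 78.81 = 0.13 | 52.01 − 50.55 = 1.46 |
| 40% | 90 d | 33.22 − 32.34 = 0.88 | 6.70 − 5.29 = 1.41 |
| 60% | 90 d | 54.10 − 53.35 = 0.75 | 22.01 − 19.48 = 2.53 |
| 80% | 90 d | 76.22 − 75.78 = 0.44 | 51.38 − 48.93 = 2.45 |

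The 40% row corresponds to −ln(0.4) = 0.92 stops per year. Over the narrower range of 0.3 to 0.8 per year and both gap wordings, the bias with 30-day fills is about 0.1 to 0.2 points at 12 months, 0.6 to 1.1 at 24 months and 0.7 to 1.5 at 3 years. With 90-day fills it is up to about 0.8 points at 12 months and 2.6 at 3 years.

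**4. Late entrants.** For patients indexed in the last 90 days, with 30-day fills and W = 90, a separate run of 400,000 patients gives at 12 months:

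- 0.3 per year: 76.0 − 72.6 = 3.4 points;
- 0.5 per year: 63.3 − 58.7 = 4.6 points;
- 0.8 per year: 48.0 − 42.5 = 5.5 points.

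With W = 60 it falls to about 2 points at the low end.

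**5. Does earlier censoring help?** Censoring at the end of follow-up minus W gave pooled 12-month values with 30-day fills of 37.60, 57.96 and 78.81, against 37.60, 57.97 and 78.81 with look-ahead. The bias is gone.

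**The case against.** **Later claims may well be read.** Section 7.4.1 says the claims database holds all prescriptions in time order, and collection starts on November 15, 2019 (section 4), 138 days after June 30, 2019. Nothing cuts the extract at June 30. A reader might infer that late stops can never be recorded, but the documents do not support that. What stands is that the visible text does not say later claims will be used to confirm gaps.

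**The year is delivered.** A reader might infer that the promised year fails. It does not: 365 calendar days are available, and the year stands for stroke/systemic embolism and bleeding. Only observability of refill-gap stops in the last entrants falls short.

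**90 days is not a document figure.** It needs the second gap wording and an assumed 30-day supply. This objection stands, so a range is given.

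**The pooled effect is small.** At 60% persistence and 7,500 patients the 95% half-width is 1.96 × √(0.6 × 0.4 / 7,500) = 1.1 points, well above the 12-month bias. The plan reports no results by index quarter, so the late-entrant figures match no planned output.

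**Unequal bias between drugs.** One might infer this if the drugs came into use at different times. The documents give no uptake dates, and 7.7 rules out treatment comparison.

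**Switches need no 60-day gap.** True, but exclusion (g) in 7.2.2 removes patients exposed to more than one anticoagulant during follow-up. Applied as written, it leaves the refill gap as the main route to a stop.

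**Conclusion.** The concern holds in limited form. The written rule dates stops back, censors everyone else at the cut-off and provides no run-out, so it biases persistence upward unless claims after the end of follow-up are read. The blind window is 60 days under one wording and 60 days plus the days' supply under the other.

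The pooled bias is minor at 12 months, and at 24 months and later it is of the order of 1 point with 30-day fills. It is about 2 to 5 points at 12 months (5.5 at the fastest rate simulated) for patients indexed in the last 90 days, with 30-day fills. About 3 to 4.5% of patients lack a full observable year if W is 60 to 90 days. These sizes rest on assumed fill lengths, constant stopping and uniform entry, none of which the documents give.

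The three end-of-follow-up wordings conflict whatever the size of the bias, because they imply different censoring dates. The point should be corrected because persistence is part of a primary objective and the remedy is cheap. It does not undermine the study.

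**What to change.** 1. State one end of follow-up in the Abstract, 7.1 and 7.2.
2. Reconcile the two gap wordings in 7.3.1 and state how days' supply is obtained for each fill.
3. Then do one of the following:
   - Read dispensing claims past the end of follow-up, solely to confirm gaps, for at least 60 days plus the longest days' supply. With an end date of June 30, 2019, claims to November 15, 2019 cover supplies up to 138 − 60 = 78 days. A cut at September 30, 2019 would cover only 92 − 60 = 32 days.
   - Censor persistence at the end of follow-up minus the gap window, and say that the last entrants have less than one year of observable persistence.

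The cost is a slightly longer extract from the same claims database, or slightly shorter observed persistence time for late entrants. Neither needs more chart review.
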